5.4.8. Efficacy Analyses

The antitumor activity of LY3435151 in combination with pembrolizumab will be assessed based on RECIST 1.1 and iRECIST, respectively.

The Kaplan-Meier method (Kaplan and Meier 1958) will be used to estimate the curves, median time, and 95% CI of time-to-event parameters such as overall survival (OS), progression-free survival (PFS), and duration of response (DoR) based on RECIST 1.1; iPFS (“i” indicates immune responses assigned using iRECIST) and iDoR based on iRECIST for each arm. Overall response rate (ORR based on RECIST 1.1 and iORR based on iRECIST), with corresponding 95% exact CI, will be summarized for each arm. The details of the efficacy parameters are described below.

5.4.8.1. Primary Efficacy Analyses

The **ORR** is defined as the number of patients who achieve a best overall response of CR or PR divided by the total number of patients treated (safety population). The ORR, with 95% CI, will be summarized for each study part. Per RECIST 1.1 criteria, ORR for the single arm treatment within each tumor type will be calculated by confirmed best responses. Therefore, best overall response will be determined from a sequence of response assessments. Two objective status determinations of CR before progression are required for a best response of CR. Two determinations of PR or better before progression, but not qualifying for a CR, are required for a best response of PR. In the case of SD, measurements must have met the SD criteria at least once after study entry at a minimum interval not less than 6 weeks \pm 7 days measured from study entry.

5.4.8.2. Secondary Efficacy Analyses

The **disease control rate (DCR)**, defined as the proportion of patients who achieved a CR or PR or stable disease (SD) out of all patients treated, will also be summarized. Per RECIST 1.1 criteria, DCR for the single arm treatment within each tumor type will be calculated by confirmed best responses. See above for the details on the calculation of best responses with confirmation.

The **DoR** is defined as the time from the date measurement criteria for CR or PR (whichever is first recorded) are first met until the first date of objective progression is observed, per RECIST 1.1 criteria, or the date of death. If a responder is not known to have died or have objective progression, then the patient will be censored at the date of last evaluable tumor assessment.

Progression-free survival is defined as the time from the date of start of treatment to the first date of the observed clinical or radiologically documented progressive disease or death due to any cause, whichever occurs first. For patients who are not known to have died or progressed as of the data inclusion cut-off date, PFS time will be censored at the date of the last objective progression-free disease assessment prior to the date of any subsequent systematic anticancer therapy. See [Table JZIA.5.2](#) for details.

Table JZIA.5.2. Progression-Free Survival Event/Censoring Scheme

Situation ^a	Event/Censor	Date of Event or Censor
Tumor progression or death	Event	Earliest date of progressive disease or death
No tumor progression and no death	Censored	Date of last adequate tumor assessment, per RECIST 1.1, or date of first dose (whichever is later) ^b
Unless		
No baseline radiologic tumor assessment available	Censored	Date of first dose
No adequate postbaseline tumor assessment available and death reported after 2 scan intervals following the first dose ^{b,c}	Censored	Date of first dose
Tumor progression or death documented immediately after 2 or more scan intervals following last adequate tumor assessment or randomization (whichever is later) ^{b,c}	Censored	Date of last adequate tumor assessment, per RECIST 1.1, or date of first dose (whichever is later) ^b
New therapeutic anticancer treatment started prior to tumor progression or death	Censored	Date of last adequate radiological assessment prior to new therapeutic anticancer therapy ^b

Abbreviations: CR = complete response; PR = partial response; RECIST = Response Evaluation Criteria in Solid Tumors; SD = stable disease.

^a Symptomatic deterioration (that is, symptomatic progression that is not confirmed per RECIST 1.1) will not be considered as tumor progression.

^b Adequate tumor assessment per RECIST 1.1 refers to an assessment with 1 of the following responses: CR, PR, SD, or progressive disease.

^c Refer to the statistical analysis plan for the definition of 2 scan intervals, including any adjustment for scan window.

Time to response (TTR) is defined as the time from the date of start of treatment to the date measurement criteria for confirmed CR or PR (whichever is first recorded) are first met. For patients who are not known to have achieved CR or PR as of the data inclusion cut-off date, TTR will be censored at the date of the last objective disease assessment prior the date of any subsequent systematic anticancer therapy.

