Urinalysis	X			X			X	See Appendix 2. If baseline laboratory tests were performed ≤3 days prior to C1D1 and the results are deemed to be clinically valid by the investigator, laboratory tests do not need to be repeated on

Procedure	All Treatment Periods (Cycle = 21 days)							Notes
	Cycle 1 (± 3 days)			Cycle 2 (± 3 days)			Cycle 3-n (± 3 days)	
Relative Day within Dosing Cycle	1	8	15	1	8	15	1	
								C1D1.
Serum or urine pregnancy test	X			X			X	See Section 8.3.4 and Appendix 2. If baseline laboratory tests were performed ≤3 days prior to C1D1 and the results are deemed to be clinically valid by the investigator, laboratory tests do not need to be repeated on C1D1.
Coagulation	See Notes							Collect as clinically indicated
Stool sample	See Section 1.3.1							Refer to Section 1.3.1 for sample collection time points
Plasma sample	See Section 1.3.1							Refer to Section 1.3.1 for sample collection time points
On-treatment tumor biopsy				X				Mandatory on-treatment biopsy on C2D1 for all patients except during dose escalation Cohorts A1, A2, and A3. See Section 8.8.
Optional tumor biopsy	See Notes							An optional tumor biopsy may be performed, if clinically feasible, after disease progression or at additional study time points, if warranted and agreed upon by the investigator and Lilly.
Radiologic imaging	See Notes							Scans will be performed and reviewed locally; done every 6 weeks ± 7 days from Cycle 1 Day 1 for 36 weeks. Afterwards, perform every 9 weeks ±7 days. The same method of assessment and technique used at baseline should be used for each consecutive assessment thereafter. RECIST 1.1/iRECIST should be used for all tumors.
AE Collection / CTCAE Grading	See Notes							CTCAE version 5.0. Evaluated at each visit and continuously throughout study. See Section 8.3 for more information about adverse events and adverse event collection.
Concomitant Medication Notation	See Notes							Evaluated at each visit and throughout study. Refer to Section 6.5 for more information about concomitant medications.
Administer LY3435151	X			X			X	Administer Q3W per Section 6.1. May be administered up to 3 days prior to scheduled visit.
Administer pembrolizumab	X			X			X	For Dose Escalation Part B and Dose Expansion Part D, administer Q3W per Section 6.1. May be administered up to 3 days prior to scheduled visit.

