No adequate postbaseline tumor assessment available and death reported after 2 scan intervals following the first dose ^{b,c}	Censored	Date of randomization (first dose for single-arm study)
--	----------	---

Abbreviations: i = immune responses assigned using iRECIST; iCR = complete response; iPR = partial response; iSD = stable disease; iUPD=unconfirmed progression; iCPD = confirmed progression; iPFS = progression-free survival; RECIST = Response Evaluation Criteria in Solid Tumors; SAP = statistical analysis plan.

^a Symptomatic deterioration (that is, symptomatic progression that is not confirmed per iRECIST) will not be considered as tumor progression.

^b Adequate tumor assessment per iRECIST refers to an assessment with one of the following responses: iCR, iPR, iSD, iUPD, or iCPD.

^c Refer to the statistical analysis plan for the definition of 2 scan intervals, including any adjustment for scan window (new anticancer therapy in SAP).

Duration of response (iDoR) is defined as the time from the date measurement criteria for iCR or iPR (whichever is first recorded) are first met until the first date that disease is recurrent or objective progression (as assessed by investigators) is observed, or the date of death from any cause in the absence of objectively determined disease progression or recurrence. Patients known to be alive and without disease progression as of the data inclusion cut-off date for a particular analysis will be censored at the time of the last adequate tumor assessment. Duration of response will follow the same censoring scheme as iPFS. Duration of response will be analyzed for the treated patients who achieve iCR/iPR as the iBOR.

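### RECIST 1.1 duration of response lacks the new-therapy and missed-scan censoring rules that govern PFS, so a responder's DoR can end later than the same patient's PFS

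*SAP*

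**What the plan says.** **DoR.** SAP 5.4.8.2 runs DoR from the first date that CR or PR criteria are met "until the first date of objective progression is observed, per RECIST 1.1 criteria, or the date of death". For a responder with neither event, "then the patient will be censored at the date of last evaluable tumor assessment". The paragraph mentions neither subsequent therapy nor gaps between scans, and does not refer to Table JZIA.5.2. Protocol 9.4.3.2 defines the DoR event in similar terms and gives no censoring rule for it.

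**PFS.** The same SAP section says that, for patients not known to have progressed or died, "PFS time will be censored at the date of the last objective progression-free disease assessment prior to the date of any subsequent systematic anticancer therapy". Table JZIA.5.2 goes further, because two of its rows turn later events into censored observations:

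- The row "New therapeutic anticancer treatment started prior to tumor progression or death" censors at the last adequate radiological assessment before the new therapy.
- Another row censors progression or death that follows two or more scan intervals without an adequate assessment, at the last adequate assessment.

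For the length of two scan intervals, the table's footnote c says: "Refer to the statistical analysis plan for the definition of 2 scan intervals, including any adjustment for scan window". That footnote is in the SAP, and the SAP gives no definition.

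**Neighbouring endpoints.** Time to response (both documents) and duration of stable disease (Protocol 9.4.3.2) are each censored at the last assessment before subsequent systemic therapy.

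**iDoR.** SAP 5.4.8.3 states "Duration of response will follow the same censoring scheme as iPFS". This sentence is in the iDoR paragraph and concerns patients whose best response is iCR or iPR.

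**The concern.** A response ends when progression or death ends it, so DoR and PFS for the same responder should normally stop on the same date, and DoR should equal PFS minus the time to response. Here the two endpoints follow different stopping rules within one section, and no reason is given. A progression or death that Table JZIA.5.2 sets aside for PFS, because another drug had been started or scans had been missed, still counts as the DoR event. A responder who remains progression-free can be followed for DoR on scans taken under another therapy.

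The SAP plans Kaplan-Meier curves, medians and 95% confidence intervals for both endpoints. In the affected patients the DoR estimate would include time after a switch of therapy or across an unobserved gap, and it would not agree with the PFS estimate reported beside it.

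**Working it through.** The plan states no event count, power or precision for DoR or PFS, so there is no figure to reproduce. The check applies the two written rules to the same hypothetical responder.

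**Inputs**
- Scan schedule, Protocol 1.3: "done every 6 weeks ± 7 days from Cycle 1 Day 1 for 36 weeks", then every 9 weeks.
- Assumed: response first met at week 6 and confirmed at week 12, which is the last adequate scan before the new therapy or the gap.
- Assumed: two scan intervals last 12, 13 or 14 weeks in the 6-weekly period, depending on the allowance for the scan window.

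**Formulas** (weeks from first dose)
- DoR = DoR end date − response date
- PFS = PFS end date − first dose (week 0)

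**A. New therapy at week 14.** The new-therapy row censors PFS at week 12 in every line.

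| What follows | DoR as written | PFS |
|---|---|---|
| Progression at week 18 | 18 − 6 = 12, event | 12, censored |
| Progression at week 24 | 24 − 6 = 18, event | 12, censored |
| Progression at week 30 | 30 − 6 = 24, event | 12, censored |
| Death at week 60, no earlier progression | 60 − 6 = 54, event | 12, censored |
| Progression-free on the new therapy at a week 36 scan | 36 − 6 = 30, censored | 12, censored |

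**B. Missed scans, no new therapy.**
- Scans at weeks 18 and 24 are missed and progression is seen at week 30. The gap is 30 − 12 = 18 weeks, which exceeds 12, 13 and 14. PFS is censored at 12 weeks under all three definitions. DoR = 30 − 6 = 24 weeks, event.
- Only the week 18 scan is missed and progression is seen at week 24. The gap is 24 − 12 = 12 weeks. With a 12-week definition, PFS is censored at 12 weeks and DoR is 24 − 6 = 18 weeks, event. With 13 or 14 weeks, PFS is an event at 24 weeks and there is no discordance. The undefined term therefore decides the result.

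**When DoR is longer than PFS as a duration.** With response at week R, last adequate scan at week L and DoR ending at week E, the condition is E − R > L, that is, E > L + R. If L = R + 6, then E must be later than week 2R + 6: week 18, 30 or 42 for R = 6, 12 or 18. Below that limit the end dates still differ, but DoR is not the longer duration. The first line of A sits exactly at the limit.

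**After alignment.** Under the Table JZIA.5.2 rules, every patient in A and the week 30 patient in B has PFS 12 weeks, censored, and DoR 12 − 6 = 6 weeks, censored. The end dates agree, and DoR equals PFS minus time to response.

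**How many patients contribute.** About 40 patients are planned in each of Cohorts D1 and D2. The documents assume no response rate. An assumed range of 10% to 30% gives 0.10 × 40 = 4 to 0.30 × 40 = 12 responders per cohort, so each responder carries visible weight in the DoR curve. The change in the median was not calculated, because it depends on the other responders' times.

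**The case against.** **Counting events regardless of later therapy is a recognised choice.** This stands as a matter of method. The plan does not present it as a choice, however, and uses the opposite convention for PFS, time to response and duration of stable disease.

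**The word 'evaluable' might exclude scans after a switch.** It is undefined, so this reading is possible. It would not close the gap, because the word applies only to responders without progression or death; later events would still count.

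**There may be few new-therapy cases.** This partly stands. The post-treatment schedule in Protocol 1.3 says that patients leave the study before a new agent is introduced, whereas Protocol 7.1 speaks of leaving study treatment. The same schedule continues scans until progression in patients who stopped treatment without it, and follows survival until death, withdrawal or loss to follow-up. These passages must be reconciled before anyone can say how often case A could arise. Case B does not depend on them.

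**DoR and PFS are not perfectly nested anyway.** The PFS text admits clinical progression, while DoR requires objective progression. Footnote a to Table JZIA.5.2 excludes symptomatic deterioration and so points the other way. This is a further reason to refer both endpoints to one table.

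**A stronger reading of the iDoR sentence.** A reader might infer that DoR and iDoR also differ on new therapy, because iDoR is tied to the iPFS scheme. The documents do not support this. Table JZIA.5.3 has no new-therapy row; the subject appears only in a parenthesis in footnote c. DoR and iDoR differ on missed scans, for which Table JZIA.5.3 does have a rule.

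**A stronger reading of the effect.** A reader might also infer that alignment would shorten the reported DoR. That does not follow. Earlier censoring removes the patient's own event, which raises the curve from that time on, but it also shrinks the risk set for events in between, which makes those drops larger. The two effects oppose each other.

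**Conclusion.** The point holds. RECIST 1.1 DoR has neither the new-therapy nor the missed-scan rule that Table JZIA.5.2 gives PFS, and nothing elsewhere in the SAP or protocol supplies them. In each discordant case the DoR end date is later than the PFS end date. In some of these DoR is also the longer duration: 24 weeks against 12 after two missed scans, and 54 weeks against 12 after new therapy and a late death. It is not longer in every case, and the documents do not show how many responders would be affected.

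The illustrations rest on the assumed response and scan dates; the week 24 example in B also rests on the assumed length of two scan intervals. DoR is a descriptive secondary endpoint with no hypothesis test, so error rates and power are untouched. What is affected is the Kaplan-Meier estimate of DoR and its consistency with PFS. The direction of any change in the median is not fixed. The change is worth making because it is cheap and removes an unexplained inconsistency.

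**What to change.** 1. In SAP 5.4.8.2 and Protocol 9.4.3.2, state that RECIST 1.1 DoR follows the event and censoring rules of Table JZIA.5.2, with time counted from the first CR or PR.
2. Define two scan intervals in the SAP, in weeks and with the window allowance, for both the 6-weekly and the 9-weekly periods. Without this, item 1 would carry an undefined rule into DoR.
3. Add a new-therapy row to Table JZIA.5.3. Otherwise item 1 would create a difference between DoR and iDoR that does not exist now.
4. Keep a DoR analysis that ignores new therapy as a named sensitivity analysis.
5. Reconcile the statements in Protocol 1.3 and 7.1 on whether patients leave the study or only study treatment before a new agent, so that it is clear what data after a switch will exist.

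The cost is a few sentences, one table row and one additional analysis. The statistical price is more censored DoR observations among what may be few responders, and hence a less precise estimate.

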5.2.2. Sample Size Determination

The primary objective of this study is to assess the safety and tolerability of LY3435151, thereby identifying and confirming the RP2D of LY3435151, to be administered as monotherapy and in combination with pembrolizumab, in patients with solid tumors associated with high TIL

positivity. The secondary objective is to evaluate PK and any observed evidence of clinical efficacy.

With at least 3 patients treated at the RP2D in the dose escalation phase and additional patients treated at the RP2D in the dose expansion phase, a total of at least 20 patients can provide adequate precision for the estimated incidence rate of the following quantities of interest:

- (1) patients having a specified AE, or
- (2) patients showing a response (partial response [PR]/complete response[CR]) to treatment

In the dose expansion phase for both TNBC and GC, approximately 16 patients in each of these 2 tumor types will be randomized with a 1:1 ratio to receive LY3435151 as monotherapy or in combination with pembrolizumab (Stage 1). The sample size of $n=16$ in each tumor type is determined in order to minimize the patients receiving monotherapy but still provide sufficient precision to evaluate the PK/PD and safety data between monotherapy and combination therapy. Following the randomization stage, approximately 32 additional patients in each of the 2 tumor types will be enrolled to receive LY3435151 in combination with pembrolizumab (Stage 2). At each interim analysis for TNBC and GC, clinical data from approximately 20 patients in the combination dose expansion (8 from Stage 1 and 12 from Stage 2) will be available to evaluate the antitumor activity of the combination therapy. If the interim results suggest continuation of enrollment for the evaluated tumor type in TNBC and GC, an additional 20 patients will be enrolled to receive combination therapy in Stage 2 in the corresponding tumor type. Therefore, a total of approximately 40 patients will be enrolled in each tumor type for the evaluation of antitumor activity of combination therapy.

In the dose expansion phase for other tumor types associated with TIL positivity, the sample size of $n=30$ in combination therapy provides data to evaluate the safety and PK/PD profile. The sample size of $n=30$ also allows to potentially assess the antitumor activity of LY3435151 in combination with pembrolizumab in tumor types other than TNBC and GC.

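### Time to response censors every non-responder at the last scan; if Kaplan-Meier is applied, as the SAP implies, the curve will exceed the ORR from the same patients

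*SAP*

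**What the plan says.** TTR is a secondary endpoint under the RECIST 1.1 antitumour objective (Protocol 3). Protocol 9.4.3.2 and SAP 5.4.8.2 give the same definition: time from start of treatment to first meeting the criteria for a confirmed CR or PR. Everyone with no such response on record at the data cut-off falls under a single rule: "TTR will be censored at the date of the last objective disease assessment". Assessments made after a new systemic anticancer therapy has begun do not count. Neither document treats progression or death separately, and neither limits TTR to responders.

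Three other provisions bear on how this will be analysed:

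- SAP 5.4.8 says that the Kaplan-Meier method "will be used to estimate the curves, median time, and 95% CI of time-to-event parameters such as overall survival (OS"), PFS and DoR, and the two iRECIST counterparts iPFS and iDoR. TTR is not named. No other method is given for it.
- SAP 5.4.8.1 sets the response rule: "Two determinations of PR or better before progression, but not qualifying for a CR, are required for a best response of PR". CR likewise needs two determinations before progression.
- SAP 5.4.8.1 defines ORR as responders "divided by the total number of patients treated (safety population"), with an exact 95% interval under SAP 5.4.8.

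**The concern.** Kaplan-Meier censoring assumes that a censored patient has the same future chance of the event as those still under observation. For TTR that fails by definition. Once a patient has progressed, the two determinations required before progression can no longer be obtained, so the chance of a first RECIST 1.1 response is zero, as it is after death. Removing such patients from the risk set as if they might still respond gives their probability to the patients who remain, and the curve rises above the true response proportion.

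What is at stake is the coherence of one secondary output. A TTR curve that levels off well above the ORR from the same treated patients has no sensible reading. The curve would also depend on how long progressors happened to be scanned, which says nothing about the drug.

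**Working it through.** **The plan's own figures.** Neither document states a TTR figure. The nearest is SAP Table JZIA.5.1, with exact limits for a response or event proportion: lower = Beta quantile 0.025 (x, n−x+1), upper = Beta quantile 0.975 (x+1, n−x). For 10/40 this gives 0.127 to 0.412 (stated 0.13, 0.41); for 5/20, 0.087 to 0.491 (stated 0.09, 0.49). All ten rows agree to two decimals.

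**Inputs from the documents.** Scans every 6 weeks to week 36 (Protocol 1.3). A repeat scan 4 to 8 weeks after first progression in clinically stable patients, not required if unstable (Protocol 8.1.1). After treatment stops, scans continue only for patients without objective progression (Protocol 1.3). In the combination cohorts, "a total of approximately 40 patients will be enrolled in each tumor type".

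**Assumptions, not in the documents.** First response seen at week 6, 12 or 18 in 60, 30 and 10% of responders. Non-responders' last scan at week 6, 12, 18, 24 or 30 in 50, 25, 12.5, 6.25 and 6.25%.

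**Formula.** 1-KM = 1 − Π(1 − d/n), where d is the proportion of the cohort responding at a scan and n the proportion still at risk; responses precede censoring at the same scan. With progression and death as competing events and every patient followed to response or one of those events, the cumulative incidence equals responders/treated.

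**True rate 20%, no further scan.**

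- Week 6: n = 1, d = 0.12, S = 0.88. Then n = 1 − 0.12 − 0.40 = 0.48.
- Week 12: d = 0.06, S = 0.88 × (1 − 0.06/0.48) = 0.77. Then n = 0.48 − 0.06 − 0.20 = 0.22.
- Week 18: d = 0.02, S = 0.77 × (1 − 0.02/0.22) = 0.70. 1-KM = 30.0%.

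**True rate 20%, every non-responder's last scan 6 weeks later.**

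- Week 6: S = 0.88; n = 0.88.
- Week 12: S = 0.88 × (1 − 0.06/0.88) = 0.82; n = 0.88 − 0.06 − 0.40 = 0.42.
- Week 18: S = 0.82 × (1 − 0.02/0.42) = 0.781. 1-KM = 21.9%.

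The same steps at the other rates give:

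| Non-responders with a further scan 6 weeks later | True 10% | True 20% | True 30% |
|---|---|---|---|
| None | 15.5% | 30.0% | 43.4% |
| Half | 12.5% | 24.8% | 36.7% |
| All | 11.0% | 21.9% | 32.8% |

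A repeat at 4 weeks leaves the first row unchanged, because it falls before the next scheduled scan; a repeat at 8 weeks gives the last row.

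**Different assumptions.** A simulation (2,000 runs per setting, n = 20 and n = 40) used responses at weeks 6, 12, 18 and 24 (45/30/15/10%), median time to progression in non-responders of 8, 12 or 24 weeks, and 0 or 50% of non-responders with one extra scan. 1-KM came out at 11–18% for a true 10%, 17–26% for 15%, 28–41% for 25% and 41–57% for 37.5%. It exceeded the true rate in every setting, by about 1 to 20 percentage points. The excess is zero only if progressors stay in the risk set until after the last response.

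**The case against.** The strongest reply is that the SAP never says TTR will be analysed by Kaplan-Meier. That is correct, and a reader who took the method as stated would be going beyond the text: SAP 5.4.8 does not name TTR, and no TTR curve, median or interval is promised. If TTR is summarised in responders alone, no bias arises. What remains is that the list is open, no other method is given, and the censoring sentence applies only to non-responders, so a responders-only summary would leave it without a function. By contrast, iDoR is expressly confined to responders (SAP 5.4.8.3); TTR is not. Kaplan-Meier is the natural reading, but it is an inference.

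The second reply concerns size. The TTR rule uses the last objective assessment, not the last progression-free one as for PFS, so the repeat scans in Protocol 8.1.1 keep progressors in the risk set longer and shrink the excess. This stands, and is why the result is a range. Not every patient will have a repeat scan, since unstable patients need none; equally, patients whose progression remains unconfirmed may have more than one.

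Third, a reader might expect a misleading median TTR. In the tabulated scenarios 1-KM peaks at 43%, so the median is simply not reached. A median does appear in an illustrative cohort with 15 responders in 40, where Kaplan-Meier gives 18 weeks although fewer than half respond, but that rests on chosen scan times.

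A late response after apparent progression does not rescue the rule: such responses belong to the iRECIST endpoints, and TTR is listed under RECIST 1.1.

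**Conclusion.** The point holds, conditional on Kaplan-Meier being used, which the SAP implies without stating. The direction is firm: if non-responders are censored for progression or death while others can still respond, 1-KM exceeds the ORR. The size is illustrative: about 1 to 3 percentage points in the tabulated scenario if every non-responder has a further scan 6 weeks later, and about 6 to 13 if none does, over true rates of 10 to 30%. Both rest on the assumed timing of responses and last scans.

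A reader might infer that the ORR or the expansion decision is compromised. The documents do not support that. ORR uses all treated patients with an exact interval and does not depend on TTR censoring. There is no formal test of response (SAP 5.2.1), and continuation of D1 and D2 rests on an overall benefit-risk review with no TTR criterion (SAP 5.8). The effect is confined to a descriptive secondary output. It should be corrected because the rule as written serves only an analysis that would mislead.

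**What to change.** In SAP 5.4.8.2, replace the TTR censoring sentence with a statement that TTR is summarised among confirmed responders only, as median and range, with no censoring. If a curve for the whole cohort is wanted, specify the cumulative incidence of confirmed response (Aalen-Johansen), with at least progression and death as competing events, and state how the start of new anticancer therapy is handled.

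Protocol 9.4.3.2 carries the same sentence. Align it at the next amendment, or describe the change in the clinical study report; Protocol 9.4.1 and SAP 5.4 require an amendment only when a principal feature changes. The cost is one SAP passage and one table or figure. No new data, patients or visits are needed.
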